9.3.2.2 AIS

With the AIS, improvement as well as worsening is included in the calculations of the sum of the items. For the items with subitems, i.e. skin toxicity and neuropsychiatric effects, only the subitem with the highest positive weight is used as well as the subitem with the lowest negative weight is used. For example: if the highest positive skin subitem is +26 and the highest negative skin subitem is -18, then skin weight for AIS is +8.

AIS is calculated at W14 and at W30 as the sum of the items in all post-baseline timepoints up to that timepoint respectively. The overall AIS is the sum over all post-baseline timepoints.

ARGX-113-1904

Statistical Analysis Plan

Final analysis

Final 2.0 of 22NOV2023

9.4 TOXICITY GRADES (CTCAE, v5.0)

Below table documents how the Common Terminology Criteria for Adverse Events CTCAE, v5.0: November 27, 2017 is implemented in the statistical analysis.

CTCAE, v5.0: November 27, 2017

PARAMETER	Unit	GRADE 1	GRADE 2	GRADE 3	GRADE 4
Amylase (pancreatic)		>1.0-1.5 *ULN	>1.5-2.0 *ULN	>2.0-5.0 *ULN	>5.0 *ULN
Alanine amino transferase		>1-3 *ULN	>3-5 *ULN	>5-20 *ULN	>20 *ULN
Albumin	g/L	<LLN-30	<30-20	<20	-
	g/dL	<LLN-3	<3-2	<2	-
Alkaline phosphatase		>1.0-2.5 *ULN	>2.5-5.0 *ULN	>5.0-20.0 *ULN	>20.0 *ULN
Aspartate amino transferase		>1-3 *ULN	>3-5 *ULN	>5-20 *ULN	>20 *ULN
Bilirubin (total)		>1.0-1.5 *ULN	>1.5-3.0 *ULN	>3.0-10.0 *ULN	>10.0 *ULN
Calcium (ionized) low	mmol/L	<LLN-1.0	<1.0-0.9	<0.9-0.8	<0.8
	mg/dL	<LLN-4.0	<4.0-3.6	<3.6-3.2	<3.2
Calcium (ionized) high	mmol/L	>ULN-1.5	>1.5-1.6	>1.6-1.8	>1.8
	mg/dL	>ULN-6.0	>6.0-6.4	>6.4-7.2	>7.2
Calcium (corrected) low	mmol/L	<LLN-2.00	<2.00-1.75	<1.75-1.50	<1.50
	mg/dL	<LLN-8	<8-7	<7-6	<6
Calcium (corrected) high	mmol/L	>ULN-2.9	>2.9-3.1	>3.1-3.4	>3.4

ARGX-113-1904

Statistical Analysis Plan

Final analysis

Final 2.0 of 22NOV2023

PARAMETER	Unit	GRADE 1	GRADE 2	GRADE 3	GRADE 4
Cholesterol	mg/dL	>ULN-11.5	>11.5-12.5	>12.5-13.5	>13.5
	mmol/L	>ULN-7.75	>7.75-10.34	>10.34-12.92	>12.92
	mg/dL	>ULN-300	>300-400	>400-500	>500
Creatine kinase		>1.0-2.5 *ULN	>2.5-5.0 *ULN	>5.0-10.0 *ULN	>10.0 *ULN
Creatinine		>1.0-1.5 *ULN	>1.5-3.0 *ULN	>3.0-6.0 *ULN	>6.0 *ULN
Gamma-glutamyl transferase		>1.0-2.5 *ULN	>2.5-5.0 *ULN	>5.0-20.0 *ULN	>20.0 *ULN
Glucose (fasting) low [1]	mmol/L	<LLN-3.0	<3.0-2.2	<2.2-1.7	<1.7
	mg/dL	<LLN-55	<55-40	<40-30	<30
Lipase		>1.0-1.5 *ULN	>1.5-2.0 *ULN	>2.0-5.0 *ULN	>5.0 *ULN
Magnesium low	mmol/L	<LLN-0.5	<0.5-0.4	<0.4-0.3	<0.3
	mg/dL	<LLN-1.2	<1.2-0.9	<0.9-0.7	<0.7
Magnesium high	mmol/L	>ULN-1.23	-	>1.23-3.30	>3.30
	mg/dL	>ULN-3.0	-	>3.0-8.0	>8.0
Potassium low	mmol/L	-	<LLN-3.0	<3.0-2.5	<2.5
	mEq/L	-	<LLN-3.0	<3.0-2.5	<2.5
Potassium high	mmol/L	>ULN-5.5	>5.5-6.0	>6.0-7.0	>7.0
	mEq/L	>ULN-5.5	>5.5-6.0	>6.0-7.0	>7.0
Sodium low	mmol/L	<LLN-130	-	<130-120	<120

ARGX-113-1904

Statistical Analysis Plan

Final analysis

Final 2.0 of 22NOV2023

PARAMETER	Unit	GRADE 1	GRADE 2	GRADE 3	GRADE 4
Sodium high	mEq/L	<LLN-130	-	<130-120	<120
	mmol/L	>ULN-150	>150-155	>155-160	>160
	mEq/L	>ULN-150	>150-155	>155-160	>160
Triglycerides	mmol/L	1.71-3.42	>3.42-5.70	>5.70-11.4	>11.4
	mg/dL	150-300	>300-500	>500-1000	>1000
Partial thromboplastin time (activated or not specified)		>1.0-1.5 *ULN	>1.5-2.5 *ULN	>2.5 *ULN	-
CD4 count	giga/L	<LLN-0.50	<0.50-0.20	<0.20-0.05	<0.05
	counts/mm ³	<LLN-500	<500-200	<200-50	<50
Fibrinogen		<1.00-0.75 *LLN	<0.75-0.50 *LLN	<0.50-0.25 *LLN	<0.25 *LLN
International normalized ratio		>1.2-1.5 *ULN	>1.5-2.5 *ULN	>2.5 *ULN	-
Lymphocytes (absolute count) low	giga/L	<LLN-0.80	<0.80-0.50	<0.50-0.20	<0.20
	counts/mm ³	<LLN-800	<800-500	<500-200	<200
Lymphocytes (absolute count) high	giga/L	-	>4-20	>20	-
	counts/mm ³	-	>4000-20000	>20000	-
Neutrophils (absolute count)	giga/L	<LLN-1.5	<1.5-1.0	<1.0-0.5	<0.5
	counts/mm ³	<LLN-1500	<1500-1000	<1000-500	<500
Platelets	giga/L	<LLN-75	<75-50	<50-25	<25
	counts/mm ³	<LLN-75000	<75000-50000	<50000-25000	<25000

ARGX-113-1904

Statistical Analysis Plan

Final analysis

Final 2.0 of 22NOV2023

PARAMETER	Unit	GRADE 1	GRADE 2	GRADE 3	GRADE 4
White blood cells	giga/L	<LLN-3	<3-2	<2-1	<1
	counts/mm ³	<LLN-3000	<3000-2000	<2000-1000	<1000

[1] Grade definition will also be applied when the fasting conditions into which the sample was drawn have not been declared (e.g. unscheduled samples, unknown), when only (a) sporadic result(s) for the parameter was (were) non-fasting (usually unscheduled samples), and in case of scheduled post-meal samples on a same day (e.g. 4 hours after dose and after a meal).

Note: In case ULN/LLN is higher/lower than the upper/lower limit of grade 1 (or even higher grades), ULN/LLN will be ignored and only the fixed values of CTCAE will be considered. In case ULN/LLN is missing, a grade will only be derived if the value leaves no doubt on which grade is to be assigned.

Statistical Analysis Plan

ARGX-113-1904

Final analysis

Final 2.0 of 22NOV2023

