ICF	informed consent form
ICH	International Council for Harmonisation of Technical Requirements for Pharmaceuticals for Human Use
IgG	immunoglobulin G
IMP	investigational medicinal product
IRR	Injection-related reaction
ISR	Injection site reaction
IV	intravenous
IVIg	immunoglobulins given intravenously
LOCF	Last Observation Carried Forward
MedDRA	Medical Dictionary for Regulatory Activities
MMRM	Mixed model for repeated measurements
NCI	National Cancer Institute
NCPD	normalized cumulative prednisone dose
NAb	neutralizing antibody
OLE	open-label extension
PD	Pharmacodynamics
PDAI	Pemphigus Disease Area Index
PK	Pharmacokinetics
PF	pemphigus foliaceus
PT	preferred term
PV	pemphigus vulgaris
rHuPH20	recombinant human hyaluronidase PH20
QoL	quality of life

	Statistical Analysis Plan	
ARGX-113-1904	Final analysis	Final 2.0 of 22NOV2023

QTc	corrected QT interval
QTcB	Bazett's corrected QT interval
QTcF	Fridericia's corrected QT interval
SAE	serious adverse event
SAF	safety analysis set
SAP	statistical analysis plan
SBP	systolic blood pressure
SC	subcutaneous
SCR	all screened participants analysis set
SD	standard deviation
SE	standard error
SGS CR	SGS Clinical Research
SOC	system organ class
SOP	standard operating procedure
STAT	statistics
TEAE	treatment-emergent adverse event
WHO-DD	World Health Organization Drug Dictionary

	Statistical Analysis Plan	
ARGX-113-1904	Final analysis	Final 2.0 of 22NOV2023

DEFINITION OF TERMS

case report form (CRF)	A printed, optical, or electronic document in which protocol required information is recorded for each study participant.
Display	Analysis table, figure or listing.
Phase	Interval of time in the planned conduct of a study that is associated with a specific purpose: for example, screening, treatment, follow-up.
IMP	Pharmaceutical form of an active ingredient or placebo, being tested or used as a reference in a clinical study.
treatment-emergent abnormality	Any post-baseline abnormality that was not present at baseline (e.g. hemoglobin normal at baseline and grade 1 post-baseline; glucose low at baseline and high post-baseline; QTcF [450; 480] ms at baseline and >500 ms post-baseline).
Complete clinical remission (CR)	The absence of new lesions and complete healing of established lesions (except for post-inflammatory hyperpigmentation or erythema from resolving lesions).

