5.2 CLINICAL LABORATORY EVALUATION

5.2.1 Available data

Per protocol, the following laboratory parameters are expected:

- Biochemistry: sodium, potassium, calcium (total), HbA1c, creatinine, creatinine clearance (adjusted for BSA), blood urea nitrogen (BUN), alanine aminotransferase (ALT), aspartate aminotransferase (AST), total bilirubin, gamma-glutamyl transferase (GGT), low-density lipoprotein-cholesterol (LDL-C), high-density lipoprotein-cholesterol (HDL-C), total cholesterol, triglycerides, C-reactive protein (CRP), alkaline phosphatase (AP), lactate dehydrogenase (LDH), uric acid, total protein, and albumin.
- Hematology: hemoglobin, hematocrit, mean corpuscular volume (MCV), red blood cell (RBC) count, platelet count, white blood cell (WBC) count with differential.
- Urinalysis: color, clarity/appearance, specific gravity, pH, protein, glucose, ketones, blood, bilirubin, urobilinogen, nitrite, leukocyte esterase, and microscopic examination of RBC, WBC, casts, crystals, and bacteria.
- Specialty laboratory parameters: apolipoprotein B (apoB), lipoprotein A, fibrinogen, von Willebrand factor, D-dimer, proprotein convertase subtilisin/kexin type 9 serine protease (PCSK9).

Normal ranges are available as provided by the laboratory.

	
Statistical Analysis Plan
	

ARGX-113-1904
	
Final analysis
	
Final 2.0 of 22NOV2023

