5.2.2 Derivation rules

Toxicity grades will be computed according to the National Cancer Institute (NCI) common terminology criteria for adverse events (CTCAE) toxicity grading list (version 5.0). The implementation of these toxicity grades for analysis is presented in appendix 9.4. Only the parameters described in appendix 9.4 will be computed, according to the declared limits for each grade.

The following abnormality categories will be defined for parameters with no toxicity grade available:

- Low: value < lower limit of normal range
- Normal: lower limit of normal range \leq value \leq upper limit of normal range
- High: value > upper limit of normal range

Notes:

- Classification will be done by using non-imputed values and limits as reported in standardized units in the clinical database: a value <X where X equals the lower limit of normal range will be classified as low. A value X with normal range <X will be classified as high.
- For the worst-case analysis visits as defined in section 2.2.5, an additional category low + high is defined in case there are both low and high post-baseline values.

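### SAP Appendix 9.4 does not grade hemoglobin, so worsening from a low baseline is not counted as treatment-emergent in the laboratory tables; high white-cell counts and total calcium also fall outside its rules

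*SAP*

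**What the plan says.** SAP 5.2.1 lists the laboratory panel. Its hematology line begins "Hematology: hemoglobin, hematocrit, mean corpuscular volume (MCV), red blood cell (RBC) count, platelet count", and its biochemistry line begins "sodium, potassium, calcium (total), HbA1c, creatinine". Calcium is therefore collected as total calcium.

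SAP 5.2.2 sets two rules. Grades follow CTCAE v5.0, with this limit: "Only the parameters described in appendix 9.4 will be computed, according to the declared limits for each grade". The fallback is introduced by "The following abnormality categories will be defined for parameters with no toxicity grade available" and consists of low, normal and high against the laboratory's normal range.

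Appendix 9.4 is the table those rules point to: "Below table documents how the Common Terminology Criteria for Adverse Events CTCAE, v5.0: November 27, 2017 is implemented in the statistical analysis". Its hematology and coagulation rows are partial thromboplastin time, CD4 count, fibrinogen, INR, lymphocytes (low and high), neutrophils, platelets and white blood cells. There is no hemoglobin row. Neutrophils, platelets and white blood cells are graded downwards only. Calcium has rows for ionized and corrected values only.

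The Definition of terms describes a treatment-emergent abnormality as follows: "Any post-baseline abnormality that was not present at baseline (e.g. hemoglobin normal at baseline and grade 1 post-baseline". Another example in the same definition is "QTcF [450; 480] ms at baseline and >500 ms post-baseline".

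SAP 5.2.3 plans two cross-tabulations against baseline, both showing treatment-emergent counts: Table 14.3.2.3 for low/normal/high abnormalities and Table 14.3.2.4 for toxicity grades.

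**The concern.** The definition of a treatment-emergent abnormality presupposes a hemoglobin grade that the operative rule in 5.2.2 and the table in 9.4 cannot produce. Appendix 9.4 also has rows for amylase, lipase, creatine kinase, magnesium and CD4 count, none of which is in the 5.2.1 panel. That pattern suggests a standard table not fitted to this trial rather than a decision to leave hemoglobin ungraded, and SAP section 6 records no such decision.

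At stake are the by-arm laboratory safety tables. A low baseline hemoglobin is plausible here. Conventional immunosuppressants and dapsone are allowed until baseline (protocol Appendix 3), and protocol 2.1 associates dapsone with hemolysis and azathioprine with bone marrow suppression. Protocol 8.3.6 puts maximum blood sampling at about 910 mL per participant outside China. Infections are the adverse events of special interest (protocol 8.4.8), which makes the absence of high white-cell counts from both cross-tabulations awkward.

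**Working it through.** No arithmetic applies: the plan states no figure on this point, and the documents give no baseline laboratory distribution. The check follows each parameter through the rules of 5.2.2, 5.2.3, 2.2.5 and the Definition of terms.

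| Course from baseline | Table 14.3.2.3 (low/normal/high) | Table 14.3.2.4 (grades) | Treatment-emergent? |
|---|---|---|---|
| Hemoglobin: normal to slightly low | Normal/Low | Absent | Yes, without severity |
| Hemoglobin: normal to far below range | Normal/Low, same cell | Absent | Yes, without severity |
| Hemoglobin: low to lower | Low/Low | Absent | No |
| White cells or neutrophils: normal to a graded low | Absent, because the parameter has a grade | Graded | Yes |
| White cells or neutrophils: normal to high | Absent, because the parameter has a grade | No grade in that direction | No |
| Total calcium: any change | Not stated; by default low/normal/high | Rows exist for ionized and corrected values only | Depends on the reading |

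**Hemoglobin.** It is in 5.2.1 and not in 9.4, so 5.2.2 sends it to low/normal/high. Low at baseline and lower afterwards is an abnormality already present at baseline, so the definition excludes it. The QTcF example shows that the same definition does count a move from one abnormal category to a worse one. With grades, a low-baseline participant would therefore be counted whenever the grade rose. With a single low category there is nothing to move to.

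**High white cells and neutrophils.** The fallback covers parameters that have no grade, not directions that have no grade. Both have low-direction grades, so the fallback does not reach their high values. The worst-case visit in 2.2.5 does not help: for graded parameters it takes the value with the highest grade, which here is the lowest count. Lymphocytes, by contrast, have rows in both directions.

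**Calcium.** Total calcium matches neither calcium row. Albumin is in the same biochemistry panel, but no section of the SAP derives a corrected value, so the corrected rows have no input.

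**Where worsening hemoglobin is still seen.**
- Descriptive statistics of values and changes by visit (Table 14.3.2.1), with the worst-case display of 2.2.5 and 2.4.3.
- Listing 16.2.8.1, for participants with any post-baseline abnormality.
- Adverse event tables. Protocol 10.4.1 collects laboratory values that have worsened and are judged clinically significant, 10.4.3 grades them by CTCAE v5.0, and SAP 5.1.3 tabulates all and grade 3 or higher events by arm.

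**The case against.** The strongest reply is that little is lost. The worst-case visit uses all post-baseline values, including unscheduled ones, and the summaries include the minimum and first quartile, so the lowest hemoglobin values can be seen by arm. A clinically important fall should become a graded adverse event. The hemoglobin example is only illustrative: the same parenthesis also uses glucose, and blood glucose is not in the 5.2.1 panel. Section 5.2.2 is the operative rule and does place ungraded parameters somewhere. Rows for uncollected parameters produce no output and do no harm. Infections are analysed directly through their system organ class, and high counts still enter the descriptive statistics.

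Much of this stands. The unused rows are harmless, the example alone would not bind the analysis, and individual falls are not hidden from the investigator or the reader. But these routes do not replace the missing one. Distribution summaries do not count participants by severity or show the shift from baseline. Listings give no by-arm count. Adverse event capture depends on investigator judgement, and protocol 8.3.6 lets an abnormal value that fits a current diagnosis be documented without being reported as an event. A graded shift table is the objective complement to that judgement, and hemoglobin is left out of it.

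**Conclusion.** The point holds within limits. Followed exactly, the SAP omits hemoglobin from Table 14.3.2.4, does not count worsening from a low baseline as treatment-emergent in Table 14.3.2.3, and discards severity for participants at any baseline level. High white-cell and neutrophil counts enter neither cross-tabulation, and the calcium rows cannot be applied to what is collected. No efficacy result, error rate or site safety procedure is affected. The size cannot be stated in participants, because the share with low baseline hemoglobin is not given.

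Two stronger readings are tempting and are not supported. A reader might infer that anaemia worsening from a low baseline is never counted anywhere; the summaries, listing and adverse event tables show otherwise. A reader might also infer that uncorrected calcium will differ between arms through albumin. That needs a correction factor and a between-arm albumin difference, and the documents give neither. Albumin also has its own grade and its own Table 14.3.2.2.

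The conclusion rests on Appendix 9.4 as it reads in the public SAP. Fibrinogen and INR follow each other directly with no page break between them, so a lost row is unlikely, but the sponsor can confirm this at once.

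**What to change.** 1. Add a hemoglobin row to Appendix 9.4 with the CTCAE v5.0 limits, and include hemoglobin in Table 14.3.2.4. This also makes the example in the Definition of terms derivable.
2. In SAP 5.2.2, apply low/normal/high in any direction for which a parameter has no grade, at least for high white blood cells and high neutrophils.
3. For calcium, either define an albumin-corrected value from the total calcium and albumin of the same sample and grade that, or state that total calcium is summarised as low/normal/high.

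All the values are already collected. The cost is a few lines of SAP text and code, and slightly longer safety output.

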9.5 SCHEDULE OF ASSESSMENTS

Trial Period	Visit Number	Trial Day/Week	Visit Window	Treatment				EoS/ED ^a	Follow-up	
				Screening	Observational visits	IMP admin only visit	Observational visits		Follow-up W34	Follow-up W38 ^e
				V1 (BL)	V2	Observational visits	IMP admin only visit	Observational visits	EoS/ED ^a	Follow-up
						Weekly on-site visits until CR ^c	Weekly home or on-site visits until CRmin ^d	On-site visits every 4 weeks until CRmin	W31	Follow-up W34
								On-site visits every 4 weeks after CRmin until W31		Follow-up W38 ^e
				D1 (W1)	D8 (W2)	D15 (W3) until CR	CR until CRmin	CR until CRmin	W31	EoS/ED +3W
				±0 days	±2 days ^f		V1 + 7 × ±2 days ^f		±2 days ^f	EoS/E D +7W
										±3 days ^f
Assessment/Procedure										
Informed consent ^g	X									
Inclusion/exclusion criteria	X	X								
DIF/histopathology ^h	X									
Concomitant therapies/procedures	X									
Kamofsky performance score	X									
Demography	X									
Height and weight ⁱ	X			X ⁱ				X ⁱ		X

Statistical Analysis Plan

ARGX-113-1904

Final analysis

Final 2.0 of 22NOV2023

Trial Period	Visit Number	Screening						Treatment						Follow-up	
		V1 (BL)	V2	Observational visits	IMP admin only visit	Observational visits		EoS/ED ^a	Follow-up						
				Weekly on-site visits until CR ^c	Weekly home or on-site visits until CRmin ^d	On-site visits every 4 weeks until CRmin	On-site visits every 4 weeks after CRmin until W31	W31	Follow-up W34	Follow-up W38 ^e					
Trial Day/Week		D1 (W1)	D8 (W2)	D15 (W3) until CR	CR until CRmin	CR until CRmin	CRmin until W31	W31	EoS/ED +3W	EoS/E D +7W					
Visit Window		±0 days	±2 days ^f		V1 + 7 × ±2 days ^f			±2 days ^f	±3 days ^f						
Physical examination and vital signs ^{g,h}		X	X	X		X	X	X	X	X					X
ECG ⁱ		X		X ^l		X ^l		X							
Medical and surgical history		X													
Randomization ^m															
Urinalysis ^{n,o}		X	X	X		X	X	X	X ^b	X					X
Urine pregnancy test ^p		X		X ^p		X	X	X	X ^b	X					X
Blood sampling:															
Active viral infection test ^q		X													
Serum pregnancy test ^r		X													
Clinical chemistry & hematology ^{s,t}		X	X	X		X	X	X	X ^b	X					X

Statistical Analysis Plan

ARGX-113-1904

Final analysis

Final 2.0 of 22NOV2023

Trial Period	Visit Number	Screening	Treatment						EoS/ED ^a	Follow-up	
			V1 (BL)	V2	Observational visits	IMP admin only visit	Observational visits	EoS/ED +3W		EoS/ED +7W	
				Weekly on-site visits until CR ^c	Weekly home or on-site visits until CRmin ^d	On-site visits every 4 weeks until CRmin	On-site visits every 4 weeks after CRmin until W31	W31	Follow-up W34	Follow-up W38 ^e	
Trial Day/Week	D1	D-21 to D-1	D1 (W1)	D8 (W2)	CR until CRmin	CR until CRmin	CRmin until W31	W31	EoS/ED +3W	EoS/ED +7W	
Visit Window	±0 days		±2 days ^f	V1 + 7x ±2 days ^f				±2 days ^f	±3 days ^f		
Anti-Dsg-1 and anti-Dsg-3 antibodies ^{g,o}	X	X	X	X		X	X	X	X ^b	X	
PK ^{j,et}	X		X ^t			X	X	X	X ^{b,t}	X	
Total IgG and IgG subtypes ^{i,ou}	X	X	X	X		X	X	X	X ^b	X	
Vaccination antibodies ^{j,ov}	X	X	X	X		X	X	X	X ^b	X	
Anti-drug antibodies ^{j,w}	X					X (every 2 weeks)	X	X		X	
IgG autoantibody subtypes/specificity and cytokines ^{j,x}	X						X	X	X ^b	X	
B- and T-cell populations ^j	X							X			
RNA transcriptional profile ^j	X							X			

Statistical Analysis Plan

ARGX-113-1904

Final analysis

Final 2.0 of 22NOV2023

Trial Period	Visit Number	Screening	Treatment					EoS/ED ^a	Follow-up	
			V1 (BL)	V2	Observational visits	IMP admin only visit	Observational visits		Follow-up W34	Follow-up W38 ^e
Trial Day/Week				Weekly on-site visits until CR ^c	Weekly home or on-site visits until CRmin ^d	On-site visits every 4 weeks until CRmin	On-site visits every 4 weeks after CRmin until W31	W31	EoS/ED +3W	EoS/ED +7W
Visit Window		D-21 to D-1	D1 (W1)	D15 (W3) until CR	CR until CRmin	CR until CRmin	CRmin until W31	W31	EoS/ED +3W	EoS/ED +7W
HLA/non-HLA genotyping ^g			±0 days	±2 days ^f	V1 + 7× ±2 days ^f			±2 days ^f		±3 days ^f
Substudies:			X	X ^z						
Skin biopsies (at selected sites) ^{j,aa}			X	X ^{aa}				X ^{aa}		
Photography (at selected sites) ^{j,bb}			X	X ^{bb}				X ^{bb}		
QoL Assessments:										
EQ-5D-5L ^{j,cc}			X	X ^{dd}		X ^{dd}	X ^{dd}	X		
ABQOL ^{j,cc}			X	X ^{dd}		X ^{dd}	X ^{dd}	X		
GTF ^j			X	X ^{ee}		X ^{ee}	X ^{ee}	X		
IMP self-administration training ^{ff}				X		X				
IMP administration ^{gg}				X	X	X			X ^b	
PDAP ^j		X	X	X	X	X	X	X	X	X

Statistical Analysis Plan

ARGX-113-1904

Final analysis

Final 2.0 of 22NOV2023

Trial Period	Screening		Treatment				EoS/ED ^a	Follow-up	
	V1 (BL)	V2	Observational visits	IMP admin only visit	Observational visits	EoS/ED ^a		Follow-up W34	Follow-up W38 ^e
Visit Number			Weekly on-site visits until CR ^c	Weekly home or on-site visits until CRmin ^d	On-site visits every 4 weeks until CRmin	On-site visits every 4 weeks after CRmin until W31	W31		
Trial Day/Week	D1 (W1)	D8 (W2)	D15 (W3) until CR	CR until CRmin	CR until CRmin	CRmin until W31	W31	EoS/ED +3W	EoS/ED +7W
Visit Window	±0 days	±2 days ^f		V1 + 7 × ±2 days ^f			±2 days ^f		±3 days ^f
Disease assessment ^{hh}		X	X		X	X	X	X	X
Prednisone taper ⁱⁱ			X	X	X	X	X	X	X
AE monitoring									

Continuous monitoring

ABQOL=Autoimmune Bullous Disease Quality of Life; admin=administration; BL=baseline; BMI=body mass index; CR=complete clinical remission; CRmin=CR on minimal therapy; D=day; DC=disease control; DIF=direct immunofluorescence; Dsg=desmoglein; ECG=electrocardiogram; ED=early discontinuation; EoC=end of consolidation; EoS=end of study; FSH=follicle-stimulating hormone; GTI=Glucocorticoid Toxicity Index; HLA=human leukocyte antigen; IgG=immunoglobulin G; ICF=informed consent form; IMP=investigational medicinal product; OLE=open-label extension; PDAI=Pemphigus Disease Area Index; PK=pharmacokinetics; RBC=red blood cells; UNS=unscheduled visit; WBC=white blood cells; W=week; V=visit

^a All participants will complete EoS/ED, which will be the end of the trial for participants who enroll in the OLE trial ARGX-113-1905. Participants who do not enroll in the OLE trial ARGX 113 1905 will complete the follow-up visits at W34 and W38.

^b In case of suspected new lesions as reported by the participants, AEs, flare or other safety reasons, participants should come to the clinic. This may require an unscheduled visit. Depending on the reason for the visit, different assessments need to be performed. See Section 8 for more information. Participants with new lesions or flare after achieving CR should return to weekly on-site visits until CR is achieved again.

^c A minimum of 6 on-site visits, V1(BL)/W1 to W6, are required before switching to home administrations, even if CR is achieved earlier than W6. The W7 visit is the first eligible "IMP administration only" visit (refer to column "Weekly home or on-site visits until CRmin"), at home or on-site, if CR is achieved between W1 and W6.

^d Home visits are allowed once participants achieve CR, but not before W7. The investigator should call the participant every 2 weeks until CRmin is achieved to confirm the participant is still in CR. On-site visits may continue at the investigator's discretion.

^e W38 (follow-up visit 2) is the end of the trial for participants who do not enroll in the OLE trial ARGX-113-1905. The W38 follow-up visit will only be required for those participants who were still receiving IMP at least once from W27 onward. For participants who ended treatment prior to W27, W34 will be the end of the trial.

^f Trial visit windows are ±2 days during the treatment period and ±3 days for follow-up visits.

Statistical Analysis Plan

ARGX-113-1904

Final analysis

Final 2.0 of 22NOV2023

^h No trial-related assessments can be initiated before the participant has provided a signed ICF.

ⁱ Only required if not available from medical history.

^j Height and weight will be measured (and BMI will be calculated accordingly) at screening, at week W15 (or the next on-site visit if W15 does not coincide with an on-site visit), and EoS/ED. Weight will also be measured if there has been an obvious change since the last measurement.

^k At visits in which IMP is administered, the assessment or procedure should be completed before dosing.

^l A complete physical examination will be completed at each on-site visit. Vital sign measurements include systolic and diastolic blood pressure, heart rate, and body temperature. Supine blood pressure and heart rate will be measured using standard equipment after at least 10 minutes rest.

^m ECG to be taken at W12. If the W12 visit does not coincide with an on-site visit, then the assessment should be performed at the next on-site visit. ECG (heart rate, PR, QT, and QRS interval) will be read centrally. QTcF and QTcB will be calculated.

ⁿ Randomization will take place on day 1 after all eligibility checks are confirmed (eg, PDAI) and before other baseline assessments are run, and prior to dosing. Urinalysis will be performed by dipstick method and will include specific gravity, pH, protein, glucose, ketones, blood, bilirubin, urobilinogen, nitrite, leukocyte esterase, and microscopic examination (if blood or protein test results are abnormal).

^o Samples will be taken every week from V1(BL)/W1 to W9 and then every 4 weeks and at the visit where CR is observed. Once CR is achieved, samples will be taken every 4 weeks at on-site visits until EoS/ED. For participants achieving CR between V1(BL)/W1 and W6, samples will be taken weekly from W1 to W6 and then every 4 weeks at on-site visits until EoS/ED.

^p A urine pregnancy test will be conducted and analyzed locally during on-site visits at least once every 4 weeks (before and after CR) and at the time of CR.

^q Viral testing for hepatitis B surface antigen (HBsAg), hepatitis B surface antibody (anti-HBs), hepatitis B core antibody (anti-HBc), hepatitis B virus (HBV) DNA, hepatitis C virus (HCV) antibodies, HCV messenger RNA (mRNA), and human immunodeficiency virus (HIV) antibodies.

^r At screening, a serum pregnancy test must be performed in women of childbearing potential or FSH test to confirm postmenopausal status.

^s Clinical blood laboratory tests will include hematology and blood chemistry at all visits and international normalized ratio (INR) or activated partial thromboplastin time (aPTT) at screening only. The hematology profile includes hemoglobin, hematocrit, mean corpuscular volume (MCV), RBC count, platelet count, WBC count with differential. The blood chemistry profile includes sodium, potassium, calcium, hemoglobin A1c (HbA1c), creatinine, creatinine clearance, blood urea nitrogen (BUN), alanine aminotransferase (ALT), aspartate aminotransferase (AST), total bilirubin, gamma-glutamyl transferase (GGT), C-reactive protein (CRP), alkaline phosphatase (ALP), lactate dehydrogenase (LDH), low-density lipoprotein cholesterol (LDL-C), high-density lipoprotein cholesterol (HDL-C), total cholesterol, triglycerides, uric acid, total protein, and albumin.

^t For PK assessment, blood samples will be taken predose (within 2 hours before the start of IMP administration at visits where IMP is administered). An additional PK sample will be taken on D3 and on D11 (± 1 day) until samples from 24 participants are obtained. At unscheduled visits blood samples for PK will only be taken if IMP is administered.

^u At screening, total IgG will be measured as part of inclusion and exclusion criteria. The pharmacodynamic (PD) biomarkers total IgG and its subtypes (IgG1, IgG2, IgG3, and IgG4) will be measured centrally from a blood sample taken predose.

^v An extra sample(s) will be taken for additional research (including vaccination antibodies and other additional research). The actual testing of vaccination antibodies depends on (a) whether a vaccination was given to the participant; (b) whether a test is available for the vaccination given to the participant; and (c) whether the sample requirements (serum, volume, frozen sample, storage duration) match the serum samples taken and reserved for this. Timepoints for analysis will be decided upon occurrence of vaccination during the study.

^w Anti-drug antibodies to efgartigimod (in serum samples) and antibodies against rHuPH20 (in plasma samples) will be tested predose every 2 weeks from V1(BL)/W1 to W9 and then every 4 weeks at on-site visits and at the visit where CR is observed. Once CR is achieved, samples will be taken every 4 weeks at on-site visits until EoS/ED. For participants achieving CR between V1(BL)/W1 and W6, samples will be taken predose at V1(BL)/W1, W3, W5, the visit

Page 9 of 28

Statistical Analysis Plan

ARGX-113-1904

Final analysis

Final 2.0 of 22NOV2023

where CR is observed, W10, and then every 4 weeks at on-site visits until EoS/ED. Neutralizing antibodies (Nab) will be tested for all confirmed positive ADA samples.

^x Blood sampling for IgG autoantibody subtypes and specificity will be taken every 4 weeks (V1[BL]/W1, W5, W9, etc) and at the visit where CR is observed. Once CR is achieved, samples will be taken every 4 weeks at on-site visits until EoS/ED. For participants achieving CR between V1(BL)/W1 and W6, samples will be taken at V1(BL)/W1, W5, the visit where CR is observed, W10, and then every 4 weeks at on-site visits until EoS/ED. Serum aliquots from all time points will be used for IgG subtype and specificity analyses. For cytokines and complementary specificity analyses, aliquots from baseline, after 4 weeks (W5), W13 (or the visit at which CR is observed if before W13), and EoS/ED will be used.

^y Samples for B- and T-cell populations and RNA transcriptional profiles will be performed at baseline, after 4 weeks (W5) and at W13 (or the visit at which CR is observed if before W13) and at EoS/ED.

^z HLA/non-HLA genotyping will be performed at baseline and D15.

^{aa} Two 4 mm skin biopsies, 1 peri-lesional and 1 non-lesional, will be collected solely based on voluntary participation at baseline and after healing of 80% of blisters (EoC) or at EoS/ED (in case EoC has not been achieved) for scientific purposes.

^{bb} Pictures of different anatomical regions may be taken per judgment of the investigator. As a guidance, time points of baseline, DC, CR and flare are indicated. Pictures may also be taken at intermediate timepoints.

^{cc} Questionnaires are to be completed prior to any other activity.

^{dd} Assessments will be performed at baseline, after 4 weeks (W5), W15, and EoS/ED visits. If the W15 visit does not coincide with an on-site visit, then the assessment should be performed at the next on-site visit.

^{ee} The GTI assessment will be performed only at baseline, W15 and EoS/ED. If W15 does not coincide with an on-site visit, then the assessment should be performed at the next on-site visit.

^{ff} Participants will be trained to self-administer IMP (foreseen in the OLE trial; not in the ARGX-113-1904 trial) during the first 4 visits as of V3 when IMP is administered; thereafter, training for self-administration is optional (only if needed).

^{ff} IMP will be administered until CRmin. To ensure proper safety monitoring, participants should remain at the site for at least 1 hour after the first administration and for 15 minutes after subsequent administrations. Participants will be released according to their clinical status. For Germany-specific monitoring instructions, refer to Section 10.16.2.1. Participants who experience treatment failure, or flare after achieving CRmin, will be allowed to roll over into the OLE trial ARGX-113-1905 earlier than W31. Participants who do not roll over into trial ARGX-113-1905 will complete the treatment-free follow-up period.

^{hh} Disease assessment parameters include disease control (DC), end of consolidation (EoC), complete clinical remission (CR), complete remission on minimal therapy (CRmin), complete remission off therapy (CROff), flare, and treatment failure. Participants who have achieved CR and have new lesions should come to the clinic for a UNS for disease assessment.

ⁱⁱ Prednisone dose tapering will begin 2 weeks after achieving CR or 4 weeks after sustained EoC (thus, no new lesions have developed for a minimum of 6 weeks and approximately 80% or more of lesions have healed).
